4.1.2. Safety Review Prior to Enrollment of Subjects with Severe Conditions at Baseline

The enrollment of critically ill hospitalized subjects will be delayed until IDMC review of the safety data from approximately 30 subjects considered to be less severe (Section 4.3).

The available safety data from subjects in this less severe population will be reviewed by the IDMC (unblinded) and GSK Safety Review Team (SRT) (blinded) after completion of study treatment. Enrollment of critically ill subjects (with normal renal function, and those with mild or moderate renal impairment) will only begin after an acceptable outcome is reported from the IDMC review of approximately 30 less severe subjects with normal renal function.

4.1.3. Study Design Change in the Event of Widespread OSV Resistance

A contingency study design is included in this protocol to facilitate rapid implementation of a global design change should widespread resistance to OSV occur during the course of the study.

If pre-defined criteria for widespread OSV resistance are met, OSV will be temporarily or permanently discontinued. Antivirals that are recommended at the time of OSV resistance will be provided as open-label treatment, and enrollment in the study will continue. The criteria for implementation of this study design change are:

- Evidence of substantial OSV resistance in circulating influenza viruses in participating countries in the relevant geographic areas reported by World Health Organization (WHO) or Centers for Disease Control (CDC), defined as $\geq 20\%$ resistance in total of all circulating strains (e.g. $\geq 50\%$ resistance in Pandemic Influenza A (H1N1) viruses which constitutes $\geq 20\%$ of circulating strains), **OR**
- WHO or CDC recommend against treatment with single agent OSV.

In the absence of recommendations from WHO or CDC, other national health agencies in participating countries may recommend against treatment with single agent OSV for influenza treatment based on resistance patterns within a specific geographical area or country, or medical consensus. In these situations, a decision on whether to put enrollment on temporary hold at impacted site(s) should be made by investigators in consultation with local institutional review boards or ethics committees (IRB/IECs) and regulatory authorities.

While rapid diagnostic tests are not widely available to determine influenza strain or resistance, some study sites will have access to local laboratories with these capabilities that could allow appropriate subjects to continue to be enrolled.

[figure not shown]
The OSV arm may be re-instated if the level of OSV resistance diminishes below the criteria defined in the protocol, and if it is appropriate to do so, based on predicted patterns of circulating influenza strains.

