6.11.2. Prohibited Medications and Non-Drug Therapies

The only approved antiviral drug permitted during the study is 75 mg OSV. All other approved or investigational influenza antiviral drugs are not permitted during the study (i.e. zanamivir, peramivir, laninamivir, amantadine, rimantadine, ribavirin, vitaglutam, umifenovir).

Immunosuppressive medications are prohibited during the treatment period including but not limited to rituximab, alkylating agents such as cyclophosphamide, nitrosoureas, platinum compounds; purine analogs such as fluorouracil; cytotoxic antibiotics such as dactinomycin, anthracyclines, mitomycin C, bleomycin, mithramycin.

Immunoglobulins are prohibited during the treatment period.

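### The example for the oseltamivir-resistance trigger in Protocol Section 4.1.3 can be met with total resistance as low as 10%, below the 20% definition it illustrates

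*Protocol*

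**What the plan says.** Protocol Section 4.1.3 is a contingency for widespread OSV resistance. It lists two alternative criteria.

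- The first begins "Evidence of substantial OSV resistance in circulating influenza viruses in participating countries" and is defined as at least 20% "resistance in total of all circulating strains". An example follows in brackets, introduced by e.g.: at least 50% "resistance in Pandemic Influenza A (H1N1) viruses which constitutes" at least 20% of circulating strains.
- The second is a WHO or CDC recommendation against OSV used as a single agent.

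The consequence of meeting a criterion is firm: "If pre-defined criteria for widespread OSV resistance are met, OSV will be temporarily or permanently discontinued". Other recommended antivirals are then supplied open-label and enrolment continues. The same criteria govern the way back: "The OSV arm may be re-instated if the level of OSV resistance diminishes below the criteria defined in the protocol", subject also to a judgement about predicted strain patterns.

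Section 6.11.2 says: "The only approved antiviral drug permitted during the study is 75 mg OSV". It bars all other approved or investigational influenza antivirals and does not refer to 4.1.3.

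Neither the rest of the protocol nor the SAP says how total resistance is to be calculated.

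**The concern.** An example attached to a definition shows the reader how to apply it. Here the natural reading makes H1N1 at least one fifth of circulating strains, with at least half of those viruses resistant. Half of one fifth is one tenth, so the example at its minimum values does not secure the 20% it is meant to illustrate.

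The sentence decides when the background antiviral is stopped in all three arms and, through the re-instatement clause, when it may return. Two people applying it to one surveillance report could reach different answers in either direction. A site that did switch would also be using a drug that 6.11.2 prohibits as written. Section 7 allows no protocol waivers except for immediate safety concerns.

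**Working it through.** **Inputs, all from Protocol Section 4.1.3 except the last**

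- Criterion: total resistance T ≥ 20%.
- Example, resistance within H1N1: r ≥ 50%.
- Example, H1N1 share of circulating strains (natural reading): s ≥ 20%.
- Resistance in the other strains, o: not given in the documents. It is treated as an assumption and varied from 0% to 20%.

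**Formula**

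T = s × r + (1 − s) × o

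**Step 1: try to reproduce the 20% from the example's minimum values.** With o = 0, T = 0.20 × 0.50 + 0.80 × 0 = 0.10. The 20% is not reproduced; the floor is 10%.

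**Step 2: let the other strains carry resistance, keeping s = 20% and r = 50%.**

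| Resistance in other strains (assumed) | Total resistance | Meets 20%? |
|---|---|---|
| 0% | 0.10 + 0.80 × 0 = 10% | no |
| 5% | 0.10 + 0.80 × 0.05 = 14% | no |
| 10% | 0.10 + 0.80 × 0.10 = 18% | no |
| 12.5% | 0.10 + 0.80 × 0.125 = 20% | yes, exactly |
| 20% | 0.10 + 0.80 × 0.20 = 26% | yes |

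The break-even is o = (0.20 − 0.10) / 0.80 = 12.5%.

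**Step 3: let the example's figures rise above their minimums, with o = 0.** The criterion then needs s × r ≥ 0.20.

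| H1N1 resistance | H1N1 share | Total | Meets the example? | Meets the definition? |
|---|---|---|---|---|
| 50% | 20% | 10% | yes | no |
| 50% | 30% | 15% | yes | no |
| 75% | 20% | 15% | yes | no |
| 60% | 30% | 18% | yes | no |
| 50% | 40% | 20% | yes | yes |
| 100% | 20% | 20% | yes | yes |

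At 50% resistance the H1N1 share must be 0.20 / 0.50 = 40%. At a 20% share, resistance must be 0.20 / 0.20 = 100%.

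**Step 4: the other reading.** Suppose the resistant H1N1 viruses themselves make up at least 20% of circulating strains. Then T ≥ 20% whatever the other strains do, and the example agrees with the definition. On this reading, however, the 50% figure adds nothing towards the criterion: 25% resistance in an H1N1 that is 80% of strains also gives 0.25 × 0.80 = 20%.

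**The case against.** The strongest reply is that there is only one trigger. The 20% total is the definition; the H1N1 text is an illustration in brackets and cannot create a second rule. This stands. A reader might infer that the protocol contains two separate triggers, or that its threshold is really 10% and so wrong by a factor of two. The documents support neither. The definition governs. The 10% is a floor, because both example figures are minimums, and it depends on an assumption about other strains that the protocol does not make. Many combinations above the minimums meet 20%.

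The verb *constitutes* is singular and can be taken with *resistance* instead of *viruses*, which gives the consistent reading in Step 4. That reading is possible but strained, and it leaves half of the example idle. It shows that the sentence is ambiguous, not that it is clear.

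The second criterion operates whatever the percentages, and 4.1.3 also provides for recommendations by national agencies. Both points are true and narrow the practical exposure. They do not settle what the first criterion requires when no such recommendation has been made.

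A reader might also infer that the inconsistency undermines the oseltamivir-based control prior. Any mismatch with that prior would follow from a switch at whatever threshold, so this sentence does not cause it. Section 9.2.1 also describes the prior as weak, with a weight of 4.

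On 6.11.2, one can argue that a specific contingency displaces a general prohibition. That is a sensible reading, but neither section says so.

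Finally, the SAP reports termination after 10 subjects, with descriptive analysis only. The practical effect in this trial is therefore small.

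**Conclusion.** The point holds as an inconsistency between a decision criterion and its own example. On the natural reading, the example can be satisfied with total resistance anywhere from 10% to just under 20%, where the definition is not met. The lower end assumes that the other strains are fully susceptible. The gap closes at the example's minimum values once the other strains are at least 12.5% resistant, and it disappears on the strained reading. The definition formally governs, so the risk is one of misapplication in stopping or re-instating OSV. The conflict between 4.1.3 and 6.11.2 is real but secondary.

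The stated power, sample size and type I error do not depend on this sentence. No view is taken on which level of resistance should trigger the change.

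**What to change.** The sponsor's clinical team should reconcile the definition and the example in Section 4.1.3 so that both express the same trigger. They should confirm that the example's figures meet the criterion at their stated minimum values. The wording should make plain whether the share refers to H1N1 as a whole or only to its resistant part, and what the example assumes about other strains. The form and level of the trigger are for that team to decide.

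Section 6.11.2 should be reconciled with 4.1.3, so that it is clear how the prohibition applies to the replacement antivirals once the contingency is in force.

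The cost is about two sentences in a protocol amendment. No re-simulation or change to the analysis is needed.

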4.2. Treatment Arms and Duration

Subjects will be randomized in a 2:2:1 ratio to receive:

- 15 mg FBE IV DNX BID +75 mg OSV BID;
- 50 mg FBE IV DNX BID + 75 mg OSV BID; or
- IV DNX placebo BID + 75 mg OSV BID

Treatment duration will be up to 5 days ([Figure 2](#)). The investigator may elect to continue open-label oseltamivir treatment. If a subject is discharged from the hospital in less than 5 days, treatment with IV DNX will discontinue, irrespective of whether the investigator elects to continue oral OSV treatment at discharge. Follow up will continue until Day 45 for all subjects.

Figure 2 Study Schematic

4.3. Type and Number of Subjects

The study will recruit adult patients with influenza infection requiring hospitalization. Influenza patients with conditions of respiratory failure requiring mechanical ventilation, chronic kidney disease, acute renal failure, sepsis, or hemodynamic instability are considered a more severe population.

For the purposes of safety monitoring, the definitions below will be used.

Less severe hospitalized subjects are those who (but not limited to):

- are hemodynamically stable;
- may require oxygenation with facemask, facetent, nasal canula, etc;
- may or may not have radiological signs of lower respiratory tract disease; or
- may have exacerbation of underlying chronic disease, including asthma, chronic obstructive pulmonary disease (COPD), or other cardiovascular conditions not leading to hemodynamic compromise.

Critically ill hospitalized subjects are those who (but not limited to):

- require CPAP (i.e. new use for respiratory distress and not for chronic purposes such as sleep apnea), BIPAP, mechanical ventilation;
- have hemodynamic instability (with or without pressor support); or
- have central nervous system involvement (eg encephalopathy, encephalitis).

A maximum of 300 subjects are planned to be enrolled in the study, depending on study dose changes implemented after each of two planned interim analyses. The first interim analyses will occur after the first flu season if there are more than 75 subjects enrolled. Additional interim analyses may be performed after approximately 50-66% of subjects have been enrolled. Completion of enrolment in this study is expected to take multiple influenza seasons in the case of no early stopping for futility or success, with a total enrollment of approximately 300 subjects.

4.4. Design Justification

This will be the first study conducted with DNX in the hospitalized influenza population. As such the study design includes stepwise enrolment of sentinel cohorts with more stringent eligibility criteria as well as enhanced safety monitoring to assess the safety and tolerability of DNX. Following acceptable outcomes from IDMC reviews, additional subjects will be enrolled in the study.

The IV formulation of the HBr salt of DNX has been developed as treatment in this study, because parenteral administration would be a preferred mode of delivery in this hospitalized population.

All treatment groups in this study will receive open-label OSV, one of the recommended antiviral treatments for this population hospitalized for influenza [CDC, 2011; WHO, 2010]. One treatment group will receive matching IV DNX placebo as a double-blind control, while receiving open label OSV.

The primary composite endpoint of Time to Clinical Resolution (TTCR) was considered following guidelines developed by the Food and Drug Administration (FDA) for treatment of seriously ill hospitalized patients with influenza. While efficacy endpoints have not been definitively validated for all types of influenza trials, TTCR incorporates FDA guidance for inclusion of clinical signs and symptoms [FDA Guidance for Industry, 2011].

A key efficacy endpoint for this study is Time to Respiratory Resolution (TTRR) and is being evaluated as a secondary endpoint. Because DNX's mechanism of action is expected to be predominantly localized to the lung, TTRR will be analyzed to assess if it is a more relevant physiological measure. In this first study with DNX (co-administered with OSV) in hospitalized influenza, safety assessments are also a key secondary endpoint.

In alignment with the mechanism of action of DNX as an anti-inflammatory agent, which impacts the host response and not as a direct-acting antiviral, virologic endpoints are

being evaluated as exploratory endpoints. Additional exploratory endpoints include biomarkers (important in influenza infection and to demonstrate target effect) and health outcomes.

[figure not shown]
4.5. Dose Justification

Two doses of DNX are proposed for evaluation in this study. The proposed doses are 15 mg and 50 mg FBE, administered twice daily as a 1 hour IV infusion.

The doses for investigation are within the clinical experience of IV DNX in healthy subjects. Clinical exposure limits will be based upon NOAEL/2 for testicular toxicity, aligned with written responses received from the United States (US) FDA's Division of Pulmonary, Allergy, and Rheumatology Products in July 2013 for GSK's development of DNX in COPD. The projected systemic exposures for both of the selected doses in DAHLIA fall below the NOAEL/2 exposure for testicular toxicity. In Study 201022 (safety, tolerability and pharmacokinetics study in healthy subjects), DNX administered as the FB formulation was well tolerated and had an acceptable safety profile, as single doses of 10 mg (1h infusion), 25 mg (1h infusion) and 100 mg (2h infusion) and as twice daily repeat doses of 25 mg and 50 mg IV infusions (given over 1 hour) for 5 days (Section 5.3.1, DNX Investigator's Brochure). When DNX was administered as the FB tablet in Study 201682 (acute uncomplicated influenza subjects), no safety concerns were identified.

In [Figure 3](#) the projected DNX concentration-time profile at steady-state for the proposed IV doses is shown with overlay of IC₅₀ and IC₉₀ for the sigmoidal PK/pharmacodynamic (PD) relationship between blood concentrations of DNX and their effect on C-X-C chemokine ligand (CXCL)-1 induced CD11b activated neutrophil levels in ex vivo blood samples (direct surrogate for CXCR2 antagonism) observed for healthy subject data pooled from Studies CX3112483 and CX3114922 (Table 4; DNX Investigator's Brochure Section 5.2.6). The data demonstrate that projected DNX levels for 15 mg and 50 mg exceed the IC₉₀ (707 ng/mL) value for on average 1 and 4 hours respectively over the dosing interval. The projected DNX blood concentrations averaged over the 12 hour dosing interval will achieve concentrations in the region of IC₇₀ and IC₉₀, and at trough IC₄₀ and IC₇₀ for 15 mg and 50 mg respectively. A level of 50-70% CXCL1-induced CD11b expression has been associated with reduction of migration of neutrophils into the lungs in preclinical inflammation models and in human experimental medicine ozone challenge studies with a related CXCR2 antagonist, elubrixin (SB-656933) [[Lazaar](#), 2011].

Figure 3 Projected Steady-state Concentration-Time Profile Over a Dosing Interval for IV DNX DNX-HBr FBE 15mg and 50mg with Overlay of IC50 and IC90 for CXCL-1-induced CD11b-activated Neutrophil Levels in Ex Vivo Blood Samples by DNX

NOTE: solid line=median population prediction; dashed lines=90% prediction interval; Projected DNX levels derived from a PK model defined for the IV data from Study 201022 (healthy subject PK study), where steady-state is projected to be reached within 3 days of repeat BID dosing, with minimal accumulation.

4.6. Benefit:Risk Assessment

Summaries of findings from both clinical and non-clinical studies conducted with DNX can be found in the Investigator's Brochure. The following section outlines the risk assessment and mitigation strategy for this protocol:

4.6.1. Risk Assessment

Potential Risk of Clinical Significance	Summary of Data/Rationale for Risk	Mitigation Strategy
Investigational Product (IP) GSK 1325756		
Reduction in Peripheral Blood Neutrophils	Peripheral neutropenia has been reported in clinical trials of other irreversible CXCR2 antagonists MK-7123 [Seiberling, 2013], SCH527123 [Nair, 2012] and AZD5069 [Kirsten, 2015]. Reduction in peripheral blood neutrophils may occur after a single dose. Peripheral blood neutrophils return to baseline approximately 24 to 48 hours after withdrawal of the CXCR2 antagonist.	Refer to the Time and Events Table (Section 7.1) for neutrophil monitoring. Peripheral blood neutrophil count of $<1.0 \times \text{Gi/L}$ is an exclusion criterion. Also, any subject that has a peripheral blood neutrophil count of $<0.5 \times \text{Gi/L}$ at two successive measures, will be withdrawn from IP and monitored until the neutrophil count returns to pre-dose levels.
Infection Risk	
Neutrophils are an important component of host defense and innate immunity. Inhibition of neutrophil migration and activation could impact host defense and innate immunity and increase the risk of bacterial super- infection or worsening influenza virus-mediated disease..
 
Nonclinical studies in mice and ferrets with two CXCR2 antagonists in the same chemical class as DNX have not shown an increase in influenza viral load [GSK Document Number YM2010/00163/07] Secondary bacterial infections after viral infection have not been directly evaluated in nonclinical studies.
	
The site will monitor adverse events, complications of influenza (such as pneumonias [bacterial, ventilator, hospitalized and community], pneumothorax, pleural effusion, ARDS, myositis, encephalitis, myocarditis, bacterial bronchitis, otitis media, sepsis, sinusitis, bacteremia) and frequency of new associated antibiotic use and clinical symptoms of subjects during treatment and post-treatment. Also chest x-ray will be obtained at baseline for clinical comparison throughout treatment.
 
Subjects will be discontinued from IP if develop significant worsening of symptoms or strong

Potential Risk of Clinical Significance	Summary of Data/Rationale for Risk	Mitigation Strategy
		suspicion or confirmation of progressive secondary bacterial infections or require antibiotics. In addition, the study has halting criteria that are part of the IDMC review.
Testicular Effects and Male Fertility	
Testicular effects were observed in preclinical studies in mice, rats and dogs. Findings in rats at ≥ 150 mg/kg/day DNX or 500 mg/kg/day DNX HBr and dogs at 30 mg/kg/day DNX included spermatid degeneration, seminiferous tubular degeneration and secondary epididymal changes after 4 weeks of dosing with irreversible seminiferous tubule degeneration with oedema and atrophy following 26 weeks of dosing in rats.
 
The male rat fertility study showed that the male rat fertility and gonadal function were affected without affecting libido or mating performance. No male-mediated fatal developmental toxicity was observed after 8 or 63 days of dosing.
 
No adverse events related to testicular effects have been reported in clinical studies dosed up to 6 months to date. Short duration of treatment (5 days) in this study is considered to have low risk of the testicular effects.
	
Systemic exposure margins for the NOAEL for reproductive effects in male rats are 15- and 50-fold from the projected mean clinical systemic exposure (AUC) at a clinical BID dose of 15 mg DNX FBE and 50 mg DNX FBE, respectively, every twelve hours.
 
Systemic exposure margins for the NOAEL for potential male-mediated developmental toxicity in rats are 57- and 191-fold from the projected mean systemic clinical exposure (AUC) at a clinical dose of 15 mg DNX FBE and 50 mg DNX FBE, respectively, every twelve hours.
 
Systemic exposure margins for the NOAEL/2 for testicular effects in the 26 week rat toxicity study are 4- and 12-fold from the projected mean clinical systemic exposure (AUC) at a clinical BID dose of 15 mg DNX FBE and 50 mg DNX FBE, respectively, every twelve hours.
 
For the short duration of treatment, this is considered sufficient to support the proposed clinical dosing regimen.

Potential Risk of Clinical Significance	Summary of Data/Rationale for Risk	Mitigation Strategy
Renal Risk	
The IV formulation of DNX contains Captisol that is renally cleared and has a potential for accumulation in renally impaired patients.
 
Healthy volunteers have been dosed in a phase 1 study with an IV DNX formulation containing higher concentrations of Captisol with no safety concerns.
	
The study has intensive renal monitoring and stepwise inclusion of subjects with normal renal function followed by subjects with mild and then moderate renal impairment after review by an IDMC. The IDMC will include an ad hoc nephrologist member if there are 10 subjects across all treatment arms withdrawn due to the renal stopping criteria or if renal expertise is needed.
 
Subjects with CrCl <30 mL/min will be excluded from the study.
 
At the current doses, the Captisol concentrations in subjects with CrCl >30 mL/min are predicted to be below that obtained clinically with marketed Captisol containing IV voriconazole.

